1.3 Significance

Early identification and treatment of active TB disease is critical to reduce transmission of TB. However, universal TB testing for newly initiating or re-initiating ART clients may result in delayed and/or decreased TPT prescribing at a time of high TB risk for PLHIV. Universal TB testing combined with universal TPT prescribing would ensure simultaneously high rates of TB prevention, testing, diagnosis, and treatment initiation for this high-risk group.

2 Methods

2.1 Study design

We are proposing a **non-randomized pilot evaluation** of a universal TPT initiation strategy within the context of TUTT implementation for PLHIV initiating or re-initiating ART. Clinics will be assigned to the novel TUTT-PT arm or standard TUTT implementation arm with the primary analysis focused on the proportion initiated on TPT within 7 days of ART start. This study will also assess the rate of new TB diagnoses, TB treatment initiation for those testing positive for TB, the prevalence of TB drug resistance at the time of TB treatment initiation, time to TPT initiation, and provider experiences with TUTT implementation and TPT provision, among others.

2.2 Study setting

This study will be conducted by PHRU in 5 public sector health facilities in the [name] district, North West province, South Africa that are participating in the Fedisa PreventTB study. As of 2016, the [name] district has a population of 742,820 with HIV prevalence estimated as 12.9%.²² The Fedisa PreventTB study was conducted in 18 public-sector health facilities providing HIV and TB related care. Thus, the PHRU team is very familiar with the study setting and has strong relationships with the provincial Department of Health, the district and sub-district offices, and the clinic managers and staff.

2.3 Study population

All adult people living with HIV who are either newly initiating or re-initiating ART will be screened for enrolment.

Inclusion criteria:

- Adults 18 years and older
- Person living with HIV newly initiating or re-initiating ART at a participating site.
- Residing within the catchment area of the clinic and willing to be followed up at telephonically or via a home visit by a study team tracer.
- Willing and able to provide their own written informed consent.

Exclusion criteria:

- Person living with HIV stable on ART.
- Not speaking any of the languages spoken by the study team

2.4 Clinic selection

Among the 18 public sector health facilities that participated in Fedisa in the [name] district, 5 will be selected to participate in the study from the list of clinics below. Clinics were chosen based on the average number of PLHIV who initiated or re-initiated ART on a monthly basis in 2021 and 2022. In order to ensure we can achieve the required sample size; we will select the larger clinics (on the basis of ART (re-)initiations) for study participation. Among the five selected clinics, two clinics will be assigned to standard TUTT implementation, and three clinics will be assigned to TUTT-PT implementation.

District	Clinic	ART initiations 2021	Mean monthly initiations 2021	ART initiations 2022	Mean monthly initiations 2022
Matlosana	Majara Sephapho	230	19.2	133	14.8
Matlosana	Orkney	207	17.25	130	14.4
Matlosana	Gateway NM Pretorius PHC	201	16.8	104	11.6
Matlosana	Kanana	194	16.2	114	10.4
Matlosana	Alabama	159	13.25	162	13.5
Matlosana	Tsholofelo	146	12.2	118	9.8
Matlosana	Empilisweni	144	12	102	11.2
Matlosana	Khuma	120	10	109	9.1

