Background: The overarching goal of this proposal is to contribute to safely increasing TB preventive therapy (TPT) uptake in the context of a new South African policy of universal TB testing at ART initiation. TB is the leading infectious cause of death globally; South Africa has one of the highest incidences of TB worldwide (513 cases/100,000 individuals in 2021).¹ TPT forms a cornerstone of World Health Organization (WHO) and South African TB control guidelines. The Fedisa PreventTB study (R01AI150432) is testing a behavioural economics approach to increase TPT prescribing to people living with HIV (PLHIV) in a cluster-randomized trial in 36 public-sector health facilities in South Africa. In preliminary analyses, we have observed overall TPT delivery reaching 51% of PLHIV (among 52,000 patients assessed). While the study is ongoing, the combined data show a marked year to year increase in TPT prescribing at ART initiation from approximately 23% in 2017 to 69% in 2022. Although receipt of TPT has increased, barriers remain.

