4.1 Data collection tools

Table 2. List of data collection tools and intended use

Name of tool	Purpose	Schedule	Study arm
Screening form (S001)	Confirm potential participant meets study eligibility criteria	Enrolment	Both
Patient enrolment questionnaire (PT001)	Baseline demographic and health data collected from study participants	Enrolment	Both
Laboratory test results (LT001)	All laboratory test results	Enrolment and 3 months after enrolment	Both
TB Follow-up Visit (PT002)	To document participant follow-up visit (sputum collection, switch from TPT to TB tx) following a positive TB test result	Following positive TB test result	Both
Health Monitoring Call (HM001)	To monitor participants for any symptoms or adverse events after starting TPT	1 month after starting TPT	Both
Medical record review (MR001)	ART history, TPT history, TB diagnoses, TB treatment initiation and regimen changes, and TPT initiation	3 months after enrolment	Both
Health care worker interview guide (IG001)	Interview guide for assessing clinic level implementation determinants	3-6 months after study initiation	Both

Participant completion form (PC001)	To document patient study completion, withdrawal, and death	As needed, and at ~3 months after enrolment	Both
-------------------------------------	---	---	------

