4.2.4 Data security

All paper study records (e.g. consent forms) will be kept in a secure location accessible only to authorized study staff, investigators, and monitors.

5 Study limitations

This study has the following limitations:

- As this is a non-randomised pilot, inferences of our results will be limited.
- Some new ART clients may be unwilling or unable to provide written informed consent to participate in the study. This may result in selection bias in our study population and limit generalizability.
- The presence of a PHRU study team research interviewer may influence routine TUTT implementation and TPT prescribing in standard of care clinics. We will minimize this influence by only enrolling participants into the study after the clinical consultation has been completed.
- Some participants may not own or have access to a mobile phone which is necessary for tracing of those who test positive for TB to initiate them rapidly on anti-TB treatment. To mitigate delays in anti-TB treatment initiation, all participants will consent to a household visit for tracing purposes if they do not have or do not answer their mobile phone.

6 Appropriate care in response to study-specific findings.

Participants in both TUTT-PT and routine TUTT implementation clinics who test positive for TB will be traced by a PHRU study team tracer and initiated on anti-TB treatment. The tracer will aim to return the participant to the clinic within 72 hours of sputum collection (48 hours for return of results and an additional 24 hours to trace the participant). The PHRU study nurse will refer participants to clinic staff for switch from TPT to anti-TB treatment in TUTT-PT participating facilities and clinic staff will initiate anti-TB treatment in routine TUTT implementation clinics. All participants who test positive for TB will be requested to provide additional sputum specimens (1) as per routine care and (2) for study-specific culture and drug susceptibility testing. Those with evidence of drug resistance will be referred to a doctor for further review and drug-resistant TB treatment initiation, as necessary.

7 Protection of human participants

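### Clinic assignment and the primary analysis state no use of parent-trial arm or prior TPT prescribing, although the parent trial targets the same behaviour as the primary outcome

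*Combined protocol and SAP*

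**What the plan says.** The front-page Background says that the parent study "is testing a behavioural economics approach to increase TPT prescribing to people living with HIV (PLHIV) in a cluster-randomized trial in 36 public-sector health facilities". Section 2.2 places this study in five facilities "that are participating in the Fedisa PreventTB study".

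On selection, section 2.4 says "we will select the larger clinics (on the basis of ART (re-)initiations) for study participation". Its table of eight candidate clinics gives ART initiation counts only. On allocation, section 2.1 describes a non-randomised pilot and says "Clinics will be assigned to the novel TUTT-PT arm or standard TUTT implementation arm"; section 2.4 adds that "two clinics will be assigned to standard TUTT implementation, and three clinics will be assigned to TUTT-PT implementation". No procedure for the assignment is given.

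Table 1 in section 2.8 lists a chi-square test for the first primary outcome, the share starting TPT within 7 days of starting or restarting ART. No covariates and no pre-study period are mentioned. Clustering appears only in section 2.9, as a design effect of about 1.3 in the sample size. Table 2 lists an enrolment questionnaire (PT001): "Baseline demographic and health data collected from study participants". Section 5 concedes: "As this is a non-randomised pilot, inferences of our results will be limited".

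**The concern.** Clinics in the parent trial were randomised to receive, or not receive, an intervention meant to change how often staff prescribe TPT. The new study measures nearly the same thing in a subset of those clinics. If more of the TUTT-PT clinics than of the standard clinics carry the parent intervention, or if they simply prescribed more TPT beforehand, that difference is counted as an effect of TUTT-PT. The reverse imbalance hides a real effect. With two clinics against three, such imbalances do not average out. The design effect allows for extra variance but not for a systematic difference between arms. The contrast at risk is the one on which the study is powered and which is meant to inform TPT policy.

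**Working it through.** **1. The plan's sample size reproduces.** Inputs from section 2.9: 65% vs 80%, 80% power, 5% level (two-sided assumed), design effect 1.3. The usual two-proportion formula gives 138 per arm, or 151 with continuity correction. Then 151 × 1.3 = 196.3, so 197, close to the stated 200. The point does not rest on a sample-size error. (Section 2.9 also gives a total of 450, which is not 200 + 200; that is a separate matter, and 200 per arm is used here.)

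**2. Bias from parent arm.** Let *e* be the parent intervention's effect on TPT, in points (not in the documents, so assumed). Let *a* of the 2 standard clinics and *b* of the 3 TUTT-PT clinics be in the parent intervention arm. With clinics weighted equally within each arm,

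bias = *e* × (*b*/3 − *a*/2).

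There are C(5,2) = 10 possible allocations. For each number *k* of parent-intervention clinics among the five, the bias in points is as follows, with the number of allocations in brackets:

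| *k* | *e* = 5 | *e* = 10 |
|---|---|---|
| 0 or 5 | 0 (10) | 0 (10) |
| 1 | +1.7 (6), −2.5 (4) | +3.3 (6), −5.0 (4) |
| 2 | −0.8 (6), +3.3 (3), −5.0 (1) | −1.7 (6), +6.7 (3), −10.0 (1) |
| 3 | +0.8 (6), −3.3 (3), +5.0 (1) | +1.7 (6), −6.7 (3), +10.0 (1) |
| 4 | −1.7 (6), +2.5 (4) | −3.3 (6), +5.0 (4) |

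Unless all five clinics share an arm, exact balance is impossible. The smallest absolute bias is *e*/6 and the largest is *e*. For *k* = 2 or 3, six of the ten allocations reach the smallest value, so knowing the parent arm before assigning makes a practical difference.

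**3. Effect on the planned test.** The inputs are 200 per arm, two-sided 5%, normal approximation, independent observations, and 65% in the standard arm.

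- TUTT-PT has no effect but its clinics start 5 points higher (65% vs 70%). The null SE is √(2 × 0.675 × 0.325/200) = 0.0468 and the alternative SE is √((0.2275 + 0.21)/200) = 0.0468. The chance of significance is Φ((0.05 − 1.96 × 0.0468)/0.0468), about 19%. With a 10-point gap it is about 59%.
- The 15-point effect is real but the gap runs against TUTT-PT. A 5-point gap leaves 65% vs 75% and power of about 59%. A 10-point gap leaves 65% vs 70% and about 19%.

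**4. Which assumed effects fit the plan's own design effect?** At 400/5 = 80 per clinic, 1.3 implies an ICC of 0.3/79 = 0.0038. The between-clinic SD at 65% is then √(0.0038 × 0.2275) = 0.029. A shift of *e* in about half the clinics gives an SD of *e*/2, so the largest shift compatible with 1.3 is about 6 points. A 10-point shift gives an SD of 5 points, an ICC of 0.0025/0.2275 = 0.011 and a design effect of 1 + 79 × 0.011, about 1.9.

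**5. Price of subtracting a clinic baseline.** Take about 130 earlier initiations per clinic; the first five clinics in the section 2.4 table averaged 643/5 = 129 in 2022. The variance of a clinic's change is 0.2275/80 + 0.2275/130 = 0.00459. Without subtraction it is 0.2275/80 + 0.00086 = 0.00370. Even if clinic differences persist perfectly, subtraction raises the clinic-level variance by about 24% under the plan's ICC.

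**The case against.** The protocol calls itself a non-randomised pilot and admits limited inference. That is fair disclosure. It is generic, though: it does not name parent-trial arm as a source of bias, and it uses none of the information that could reduce it.

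A reader might infer that the clinics are assigned by hand with the parent arm deliberately ignored. The documents give no assignment method, so only *not stated* is supported. A reader might also infer that each clinic's earlier TPT rate is already known. The Background gives aggregates only: 51% overall, and about 23% in 2017 rising to 69% in 2022. Clinic-level figures are plausible from a trial that assessed some 52,000 patients, but they are not shown.

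Nor is a live parent effect established. The Background and section 1.1.4 describe the parent study as ongoing or active, while sections 2.2 and 2.4 also speak of it in the past tense. Which of the five clinics received its intervention, and whether it continues during recruitment, is not stated.

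Finally, a change-from-baseline estimate has costs beyond noise. Its baseline would cover all initiators at a clinic, whereas the study outcome is in consenting participants. It may also predate the 2023 TUTT policy, in a period when TPT was rising steeply. These objections stand, and they argue for a supporting role rather than a new main estimate.

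**Conclusion.** The point holds as a gap in the plan: followed as written, it can confound the first primary contrast and offers no means of seeing whether it has. The size and direction of any bias are unknown. The ranges in the brief rest on an assumed parent effect and on equal weighting of clinics within each arm.

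A reader might infer a 10-point bias in favour of TUTT-PT, two-thirds of the hypothesised 15 points. The documents do not support that. It needs an assumed 10-point effect, larger than the roughly 6 points that fit the plan's own design effect (itself unsupported). It also needs the most extreme allocation, 1 of 10 when three of the five clinics are in the parent intervention arm, and the sign could equally be negative. A 5-point gap is the more restrained illustration, and even that raises the chance of a false positive to about 19%.

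**What to change.** Before assignment, tabulate for the eight listed clinics the parent-trial arm and, where retrievable from parent-trial or routine records, the latest pre-study TPT proportion on the same 7-day definition. Choose the five clinics and the 2:3 allocation so that parent arm is as balanced as possible, with prior TPT proportion as the second criterion. If more than one acceptable allocation remains, draw among them at random. Report both items by clinic with the results.

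Keep the planned unadjusted comparison. Pre-specify two supporting analyses: the difference between arms in each clinic's change from its own pre-study TPT proportion, and an estimate adjusted for participant baselines such as age, sex, ART-naive vs re-initiating, and symptoms. The protocol does not itemise PT001, so its fields should be confirmed. The second analysis addresses participant mix; it does not remove a parent-arm difference.

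The cost is one short table and modest extra analysis. The downsides are that few allocations may qualify, and that the baseline-change estimate is noisier and has the population and policy-period limits noted above. If assignment has already been made, the table and the supporting analyses are still possible.

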2.5 TUTT-PT (intervention) arm

In the TUTT-PT arm, newly initiating or re-initiating ART clients will be referred by clinic staff after ART initiation to the PHRU study nurse for eligibility screening and enrolment. All TUTT-PT arm participants who provide written informed consent will have sputum collected for TB testing (if sputum was not already collected by the clinic staff) and will receive a clinical evaluation for the presence of TB symptoms (cough, fever, weight loss, night sweats) and serious contraindications for TPT initiation (known liver disease, high alcohol intake (men: >5 drinks/day or >15 drinks/week; women: >4 drinks/day or >8 drinks/week), or strong clinical suspicion of TB disease as evidenced by severity of symptoms, including haemoptysis, or Karnofsky score ≤ 50). PLHIV for whom the study nurse does not have a strong clinical suspicion of TB nor evidence of serious TPT contraindications will be referred to clinic staff for TPT initiation, irrespective of the presence or absence of TB symptoms.

2.6 Standard TUTT implementation arm

In the standard TUTT implementation arm, ART clients who initiated or re-initiated ART will be referred to the PHRU study nurse for eligibility screening, enrolment, and a clinical evaluation after the consultation has been completed. All laboratory investigations and ART and TPT prescribing will occur as per routine care in the facility prior to referral to the PHRU study nurse who will obtain written informed consent for study participation.

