2.8 Outcomes and analysis

The primary outcomes are the proportion of PLHIV who initiate TPT within 7 days of ART start and the median time to TB treatment initiation for those who test positive for TB. ART initiators include clients who are ART naïve and those re-initiating ART after a lapse in treatment. Secondary outcomes are included in the table below. TB test results and TPT initiation will be ascertained from study source documents and all available data sources in the clinics, including but not limited to paper files, electronic files (Tier.NET and DHIS2), clinic registers, pharmacy records, and lab test results. Analytic approaches are described in the table below.

Table 1. Outcomes & analysis approach

	Outcomes	Data source	Statistical Test
Primary	Proportion of PLHIV who initiate TPT within 7 days of ART (re-)initiation	Paper files, electronic files, clinic registers, pharmacy records, lab test results	Chi-square
Primary	Proportion of PLHIV who initiate TPT and have a subsequent positive TB test result	Paper files, electronic files, clinic registers, pharmacy records, lab test results	Chi-square
Primary	Healthcare provider experiences with universal TB testing and TPT provision	In-depth interviews	N/A
Primary	Median time to TB treatment initiation for those who test positive for TB	Paper files, electronic files, clinic registers, pharmacy records, lab test results	Kaplan-Meier
Secondary	Proportion of PLHIV evaluated for ART (re-)initiation tested for TB within 7 days of ART start, stratified by TB symptom status	Paper files, electronic files, clinic registers, pharmacy records, lab test results	Chi-square
Secondary	Prevalence of active TB disease among PLHIV evaluated for ART (re-)initiation, stratified by symptom status	Paper files, electronic files, clinic registers, pharmacy records, lab test results	Chi-square
Secondary	Median time from ART initiation to TPT initiation	Paper files, electronic files, clinic registers, pharmacy records, lab test results	Kaplan-Meier
Secondary	Proportion of PLHIV diagnosed with TB who remain on TPT for 7 days or longer	Paper files, electronic files, clinic registers, pharmacy records, lab test results	Chi-square
Secondary	Prevalence of TB drug resistance at TB treatment initiation, stratified by TPT use at the time of TB diagnosis	Paper files, electronic files, clinic registers, pharmacy records, lab test results	Descriptive proportions

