Written informed consent will be obtained from eligible patient participants and from health worker participants at times convenient to them. The consent process will be done in a private area to ensure confidentiality. Informed written consent, using Ethics Committee/IRB-approved consent forms, will be obtained by trained study personnel prior to performing any study-specific procedures. Informed consent is a process that will be initiated prior to the individual's agreeing to participate in the study and will continue throughout the individual's study participation. Potential participants will receive information about risks and possible benefits of study participation, study objectives, and procedures. Informed consent requires the legally effective signature or mark of the subject. A copy of the signed and dated informed consent document will be offered to each participant for his or her records. The rights and welfare of the subjects will be protected by emphasizing to subjects that the treatment by health care providers will not be adversely affected if they decline to participate in this study, and that they may withdraw consent at any time. The investigator will retain a copy of the signed consent forms, which may be inspected at the monitor's/auditor's request. The investigator will promptly report to the Ethics Committee/IRB of all changes in the research activity and all unanticipated problems involving risks to human subjects or others, and will not make changes in the research without Ethics Committee/IRB approval, except where necessary to eliminate apparent immediate hazards to human subjects.

The informed consent process will include a verbal review of the study, provision of participant information sheets in relevant languages, review of the information sheets, and answering any questions. Participants unable to read or write will be asked to make a mark or thumbprint in the presence of a witness (verbal consent will not be obtained). Only written informed consent will allow for study participation.

Health care worker participation

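### Consent comes before the TPT step in TUTT-PT clinics but after TPT prescribing in standard clinics, so selection into the 7-day TPT comparison can differ by arm

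*Combined protocol and SAP*

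**What the plan says.** **TUTT-PT clinics (Section 2.5).** Here "newly initiating or re-initiating ART clients will be referred by clinic staff after ART initiation to the PHRU study nurse for eligibility screening and enrolment". After written consent come sputum collection, if not already done, and a clinical evaluation. Clients without strong suspicion of TB or a serious contraindication then "will be referred to clinic staff for TPT initiation, irrespective of the presence or absence of TB symptoms". No TPT step is described before consent.

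**Standard clinics (Section 2.6).** "All laboratory investigations and ART and TPT prescribing will occur as per routine care in the facility prior to referral to the PHRU study nurse". Consent comes only after that, and it is this nurse "who will obtain written informed consent for study participation".

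**Who is counted.** Section 2.3 makes consent an inclusion criterion in both arms: "Willing and able to provide their own written informed consent". Section 7.4 adds: "Only written informed consent will allow for study participation". Willingness to take TPT is not a criterion. The outcome in Table 1 is "Proportion of PLHIV who initiate TPT within 7 days of ART (re-)initiation", tested by chi-square. The denominator is not defined further. That it means consenting participants is a strong inference from the consent rule and the enrolment target.

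**What is acknowledged.** Section 5 says of clients who do not consent: "This may result in selection bias in our study population and limit generalizability". It also gives late enrolment in standard clinics as a way to limit the study's influence on routine prescribing. It does not mention that consent and TPT come in a different order in the two arms.

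**The concern.** The primary comparison concerns TPT uptake. In TUTT-PT clinics, consent is the route to the study's same-day TPT referral, so a client who does not want TPT has a direct reason to refuse the study. In standard clinics the TPT decision has already been made, and consent adds no TPT commitment. If would-be non-starters decline more often in one arm, they leave that arm's denominator and its uptake rises with no change in what the strategy achieves. A test or model fitted to enrolled participants has no information on those who never enrolled. Section 1.1.4 intends the comparison to inform TPT policy, so an artefact of a few points in its main contrast matters.

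**Working it through.** **1. The plan's own figure.** Inputs from Section 2.9: 65% versus 80%, 80% power, 5% level (two-sided assumed), design effect about 1.3.

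- n per arm = [1.96 × √(2 × 0.725 × 0.275) + 0.8416 × √(0.65 × 0.35 + 0.80 × 0.20)]² / 0.15² = 138.
- With continuity correction, n = 151, and 151 × 1.3 = 196.3, so 197. This reproduces the stated 200 per arm. Without the correction, 138 × 1.3 = 179.4, so 180.
- Section 2.9 also gives a total of 450, while 200 + 200 = 400. That needs reconciling separately. I use 200 per arm.

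**2. Effect of selection in one arm.** Let u be true uptake among all eligible clients and q the share of would-be non-starters who decline the study. If all would-be starters enrol:

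observed uptake = u / [u + (1 − u)(1 − q)]

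The protocol gives no refusal rate, so q is an assumption. With u = 65% in both arms and q = 0 in standard clinics:

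| q in TUTT-PT | Calculation | Observed | Bias (points) | Decliners as share of all clients |
|---|---|---|---|---|
| 10% | 0.65/0.965 | 67.4% | +2.4 | 3.5% |
| 20% | 0.65/0.930 | 69.9% | +4.9 | 7.0% |
| 30% | 0.65/0.895 | 72.6% | +7.6 | 10.5% |

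With about 154 effective participants per arm (200/1.3), the chance of a significant result favouring TUTT-PT when there is no true effect is about 6%, 15% and 30% respectively. Without selection it would be 2.5%.

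**3. What would create the whole planned difference.** Moving 65% to 80% needs 1 − 0.65/0.80 = 18.75% of all TUTT-PT clients to decline because of TPT. That is 0.1875/0.35 = 53.6% of non-starters, which is a demanding assumption.

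**4. Selection in both arms.** Same formula, u = 65%:

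| q TUTT-PT | q standard | Bias in the difference (points) |
|---|---|---|
| 20% | 20% | 0 |
| 20% | 10% | +2.5 |
| 10% | 20% | −2.5 |

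The sign depends on the contrast between arms, not on refusal in TUTT-PT alone.

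**5. How decliner bounds behave.** Suppose the planned rates are observed: 160/200 and 130/200. Let d eligible clients decline in each arm.

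- Least favourable to TUTT-PT (its decliners not started, standard-arm decliners started): 160/(200 + d) versus (130 + d)/(200 + d). The difference reaches zero at d = 30, which is 30/230 = 13.0% of eligible clients.
- All decliners not started, d = 30: 160/230 = 69.6% versus 130/230 = 56.5%, a difference of 13.0 points.

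The least favourable case is severe, so both belong in the report.

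**6. Could a clinic-wide denominator replace the enrolled one?** Using the 2022 monthly means in Section 2.4 and the four recruitment quarters in Section 3:

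- Three smallest listed clinics: 9.1 + 9.8 + 10.4 = 29.3 a month, × 12 = 352.
- Largest three of the first five listed: 14.8 + 14.4 + 13.5 = 42.7 a month, × 12 = 512.

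With 200 enrolled in TUTT-PT clinics, 1 − 200/352 = 43% to 1 − 200/512 = 61% of initiators there would be outside the study. This assumes recruitment over the full period at 2022 volumes.

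**The case against.** A reader might infer that clients unwilling to take TPT can leave only the TUTT-PT denominator, so the error must favour TUTT-PT. The documents do not support that.

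- Consent is required in both arms. Standard-clinic clients who refused or were not prescribed TPT can also decline.
- Standard-clinic staff can know the TPT decision when they refer. If they refer TPT takers more readily, standard-arm uptake rises and the bias runs against TUTT-PT.
- A TUTT-PT client who consents and later refuses TPT stays in the enrolled set.
- Section 9 pays R150 per in-person contact in either arm, a reason to consent whatever one thinks of TPT.
- Section 7.2 shows that TPT before the test result is a known part of the intervention, so TPT-driven refusal is possible. Its extent is unknown.

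Large examples are also easy to construct. With 70% true uptake, 12.5% of all TUTT-PT clients declining gives 0.70/0.875 = 80.0%. That looks modest, but it means 0.125/0.30 = 41.7% of non-starters refuse the study for this reason, with none doing so in standard clinics.

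Nor is Section 5 silent. It concedes selection bias as well as limited generalisability, says a non-randomised pilot supports limited inference, and gives a legitimate reason for late enrolment in standard clinics.

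These points rule out certainty about direction and size. They do not answer the core issue: the order differs by arm, selection can therefore differ by arm, and nothing planned would detect or bound it.

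**Conclusion.** The concern holds in a limited form. The different order of consent and TPT is explicit, it bears on a primary outcome, and Section 5 covers non-consent only in general terms. Inflated TUTT-PT uptake is the most plausible direction, not an established one. The bias is +2.4 to +7.6 points if true uptake is 65% in both arms, 10% to 30% of TUTT-PT non-starters decline, and no standard-arm non-starters do. It is zero if refusal among non-starters is equal, and negative if it is higher in standard clinics. All these refusal rates are assumptions.

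A reader might also infer that a clinic-wide proportion should become the effectiveness result. It should not. Section 2.5 delivers the strategy through the study nurse after consent, so the 43% to 61% of TUTT-PT clinic initiators who could be unenrolled are not described as receiving it. The figure would largely measure enrolment coverage. In standard clinics everyone receives routine care, so there a gap between clinic-wide and enrolled uptake would be informative about selection.

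**What to change.** Keep the enrolment procedure and the enrolled-participant primary analysis, and make these changes:

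1. **Section 2.8:** state that the primary denominator is enrolled, consenting participants.
2. **Screening form and recruitment logs, both arms:** record eligible clients referred, those who decline, and their reasons.
3. **Table 1:** add a sensitivity analysis of the 7-day TPT proportion with decliner bounds in both arms. Include the case least favourable to TUTT-PT: its decliners counted as not started, standard-arm decliners as started.
4. **Supporting figure, subject to ethics approval:** report by arm the 7-day TPT proportion among all ART (re-)initiators at the five clinics, from de-identified aggregate counts in the sources listed in Section 2.8. Say that it does not replace the primary result, because it includes clients never offered the strategy. It also gives some view of non-referral, which the decliner bounds do not cover.
5. **Section 5:** name the arm-specific bias. State that a TUTT-PT advantage that does not survive the bounds will be reported as not robust to selection at consent. That wording does not mean that the advantage is absent.

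The cost is a little more logging, one extra table, possible ethics approval for the counts, and a possibly less favourable headline. No new visits are needed.
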